7.1 Inclusion criteria

Eligibility of study subjects shall be determined in accordance with the following criteria.

1. Patients diagnosed as type 2 diabetes.
2. Patients with a stable diet and exercise therapy only for at least 12 weeks prior to the start of the screening period.
3. Patients who require a DPP-4 inhibitor treatment.
4. Patients with HbA1c $\geq 6.5\%$ and $< 10.0\%$ at the start of the screening period.
5. Patients who completed DTR-QOL questionnaire at the start of the screening period.
6. Patients who have received less than 2 types of medication for treatment of comorbidities (such as hypertension or dyslipidemia) at the start of the screening period (any number of daily doses).
7. Patients who, in the opinion of the principal investigator or the investigator, are capable of understanding the content of the clinical study and complying with the study protocol requirements.
8. Patients who can provide the written informed consent prior to the initiation of any study procedures.
9. Patients aged ≥ 20 years at the time of informed consent.
10. Outpatient.

[Rationale for the inclusion criteria]

1-3: These were set to specify a study subject applicable to achieve objective of this study.

4: The lower and upper limits were set to include a study subject whom treatment with oral glucose-lowering medications is considered to require and who is suitable for glucose-lowering monotherapy.

5: This was set because total score of DTR-QOL questionnaire at the start of the screening period is stratifying factor of randomization.

6: This was set to minimize influences on drug taking behavior by medications for comorbidities in the QOL study.

7-10: These were set as fundamentals for this study.

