9.1.9 DTR-QOL Questionnaire

Subjects will answer the DTR-QOL Questionnaire (all 29 questions)⁵⁾ regarding the diabetes therapy being conducted at each assessment time point during the screening period and treatment period. The investigator will instruct the subjects to answer all questions truthfully and record the answer of each question of the DTR-QOL Questionnaire (29 questions in total) on the CRF.

[Calculation of the total score based on answers of the DTR-QOL Questionnaire]

- Calculation method of the total score of Factor 1: "burden on social activities and daily activities" (13 questions in all)

Every score of the question number 1-13 will be simply added up, and the total figure will be subsequently converted to percentage [the best (91) and worst (13) scores will be equivalent to 100% and 0%, respectively].

- Calculation method of the total score of Factor 2: "anxiety and dissatisfaction with treatment" (8 questions in all)

Every score of the question number 14 and 19-25 will be simply added up, and the total figure will be subsequently converted to percentage [the best (56) and worst (8) scores will be equivalent to 100% and 0%, respectively].

- Calculation method of the total score of Factor 3: "hypoglycemia" (4 questions in all)

Every score of the question number 15-18 will be simply added up, and the total figure will be subsequently converted to percentage [the best (28) and worst (4) scores will be equivalent to 100% and 0%, respectively].

- Calculation method of the total score of Factor 4: "treatment satisfaction" (4 questions in all)

Each score of the question number 26-29 will be converted into reverse (i.e., 1 will be converted to 7, 7 will be converted to 1, and so on. The converted scores, where 7 is the best and 1 is the worst, have the opposite sequence of the original scores). Then, the converted scores will be simply added up, and the total figure will be subsequently converted to percentage [the best (28) and worst (4) scores will be equivalent to 100% and 0%, respectively].

- Calculation method of the total score of all questions

Each score of the question number 26-29 will be converted into reverse, as described above, and then these converted scores and original scores of the question number 1-25 will be simply added up. Subsequently, the total figure will be converted to percentage [the best (203) and worst (29) scores will be equivalent to 100% and 0%, respectively].

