9.2.1 Screening period (Week -4)

After obtaining informed consent, the physical examination and tests will be performed for the determining eligibility for study enrollment. The eligibility of a patient will be determined based on the inclusion/exclusion criteria presented in the section 7.0. Refer to the section 9.1.16 for the preparation of records on a study subject withdrawn from the study before randomization.

Tests, observations and evaluations performed at the start of the screening period (Visit 1: Day -29 to -1) are shown below.

- Informed consent
- Inclusion/ exclusion criteria
- Demographic data, medical history
- Physical examination*
- Height, body weight and BMI
- Concomitant drugs*
- Comorbidity*
- Laboratory tests (HbA1c only) *
- DTR-QOL Questionnaire*
- The Basic Information on Study Subject (Your Basic Profile)*

*: To be performed during from Day -29 until Day -14.

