13.1.3 Efficacy analysis

From FAS the following shall be analyzed.

<Primary endpoint>

Change from baseline (Week 0) in total score for all question items in the DTR-QOL Questionnaire at the end of the treatment period (Week 12).

- 1) A comparison between the treatment groups will be carried out based on the ANCOVA model using "the change in the total score by the end of treatment [the end of the treatment period - baseline (Week 0)]" as a dependent variable; "the total score at the baseline, the total score of the DTR-QOL Questionnaire (<80% or ≥80%) at the start of the screening period and HbA1c (<8.0% or ≥8.0%) at the start of the screening period as covariates; and "a treatment group" as an independent variable. The level of significance will be 5% (two-sided).

<Secondary endpoints>

Efficacy endpoints:

- Changes in the total score for each factor provided through the DTR-QOL Questionnaire [“Factor 1: Burden on social activities and daily activities (13 questions in all)”, Factor 2: Anxiety and dissatisfaction with treatment (8 questions in all), “Factor 3; Hypoglycemia (4 questions in all)”, and “Factor 4: Treatment satisfaction (4 questions in all)”] at each assessment time point.
- Change in the total score for all questions in the DTR-QOL Questionnaire at each assessment time point.
- Change in the total score for treatment satisfaction in the DTSQ (evaluated with the score of questions #1, 4, 5, 6, 7, and 8) at each assessment time point.
 - 1) Summary statistics [sample size, mean, standard deviation (SD), maximum, minimum and quantile] and the two-sided 95% confidence interval (CI) for means per treatment group at each assessment time point will be calculated to plot the changes in means and SDs. Point estimates and the two-sided 95% CI for differences between the treatment groups will also be calculated.
 - 2) Changes from the baseline (Week 0) to each assessment time point will be calculated to be similarly analyzed to 1) above.

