End of Study	The latest date in treatment period	21～97

2) DTSQ, Laboratory Test (except HbA1c)

Analysis Visit	Reference Day	Time Allowance (Number of Study Days)
Week -4	-30	-30～-2
Week 0	-1	-1
Week 4	28	21～35
Week 12	84	70～97
End of Study	The latest date in treatment period	21～97

OTHER DATA HANDLING

Items	Method	Conditions
DTR -QOL Questionnaire Factor1: Burden on Social Activities and Daily Activities	The sum total of questions number 1 -13 was converted into a 0 -100 score [the best (91) = 100 and worst (13) = 0].	For a factor with <50% missing data, the mean value (round off 2 digits) calculated from available answers is applied to cover the missing data.
DTR -QOL Questionnaire Factor 2: Anxiety and Dissatisfaction with Treatment	The sum total of questions number 14 and 19 -25 is converted into a 0 -100 score [the best (56) = 100 and worst (8) = 0].	For a factor with <50% missing data, the mean value (round off 2 digits) calculated from available answers is applied to cover the missing data.
DTR -QOL Questionnaire Factor 3: Hypoglycemia	The sum total of questions number 15 -18, and is converted into a 0 -100 score [the best (28) = 100 and worst (4) = 0].	For a factor with <50% missing data, the mean value (round off 2 digits) calculated from available answers is applied to cover the missing data.
DTR -QOL Questionnaire Factor 4: Treatment Satisfaction	Each score of question number 26 -29 is reversed (i.e., 1 converted to 7, 7 converted to 1, and so on; the converted scores, where 7 is the best	For a factor with <50% missing data, the mean value calculated from available answers is applied to cover the missing data.

Items	Method	Conditions
	and 1 is the worst, had the opposite sequence of the original scores). The converted scores are then added up, and the total is converted into a 0 -100 score [the best (28) = 100 and worst (4) = 0].	
DTR -QOL Questionnaire Total Score of all Questions	1) Each score of question number 26 -29 was reversed.((i.e., 1 converted to 7, 7 converted to 1, and so on;). Factor1 – Factor 4 are calculated as described above.(Not converted) 2) Factor 1 - Factor 4, which calculated by the method described above, are subsequently added up, and converted into a 0 -100 score [the best (203) = 100 and worst (29) = 0].	The total score of whole questions is not calculated if a total score of any of the four factors was unavailable.
DTSQ Total Score	Item 1, 4, 5, 6, 7, 8 scores are added up,	All data must not be missing.

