2 EFFICACY EVALUATIONS

2.1 Primary Endpoint and the Analytical Methods

Analysis Set: Full Analysis Set

Items: Change from Baseline in DTR-QOL Total Score at End of Study (Week 12)

Method: Analysis of covariance (ANCOVA) is conducted to compare between the treatment groups using "Change from baseline in DTR-QOL total score by the end of treatment [the End of Study (Week 12) - baseline (Week 0)]" as a dependent variable; DTR-QOL Total Score at the start of the screening period(<80 or ≥ 80) and HbA1c ($<8.0\%$ or $\geq 8.0\%$) at the start of the screening period as covariates; and "treatment group" as an independent variable. The level of significance is defined as 5% (two-sided).

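### The screening DTR-QOL score enters the primary ANCOVA only as below or at least 80; adding its continuous value could bring a small gain in precision

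*SAP*

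**What the plan says.** SAP 2.1 lists two covariates for the primary ANCOVA of change in DTR-QOL total score: "DTR-QOL Total Score at the start of the screening period" as below 80 or at least 80, and screening HbA1c cut at 8.0%. It does not list the Week 0 total score.

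Protocol 13.1.3 lists three: "the total score at the baseline, the total score of the DTR-QOL Questionnaire" in the same two categories, and HbA1c in two categories, the last two taken "at the start of the screening period as covariates". So the protocol has the Week 0 score and SAP 2.1 does not. In neither document does the screening score enter as a number, and no sensitivity model uses it that way.

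The number exists. Protocol 9.1.9 has subjects answer all 29 items "at each assessment time point during the screening period and treatment period". Inclusion criterion 5 (protocol 7.1) admits only "Patients who completed DTR-QOL questionnaire at the start of the screening period". Protocol 9.2.1 times the screening questionnaire: "To be performed during from Day -29 until Day -14". The SAP's data-handling table states that the four factor sums are "subsequently added up, and converted into a 0 -100 score". Protocol 7.3 prohibits other diabetic drugs from Week -4, and 9.2.2 has study drug first prescribed at Week 0, so the screening score is a pre-drug value. The rationale in protocol 7.1 and the allocation rule in 8.5 explain the cut: the category is a randomisation stratum.

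**The concern.** Two measurements of the same outcome before treatment can predict the Week 12 score better than one, because each carries its own measurement error. Cutting one of them at 80 keeps only part of what it holds. Protocol 13.1.3 keeps the Week 0 score whole, so what is unused there is whatever the screening score says beyond the Week 0 score and the category.

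At stake are the width of the confidence interval for the arm difference and some protection against chance imbalance. No new data are needed. The question is whether the gain is large enough to exceed the degree of freedom that it costs.

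**Working it through.** **The plan's own figure.** Inputs from protocol 13.3: difference 19.0 - 14.4 = 4.6 points, SD of change 12.1, two-sided 5%, power 80%.
- Normal approximation: n = 2 × (1.960 + 0.842)² × (12.1/4.6)² = 108.6, so 109 per group.
- The t-test version gives 110 per group (power 80.1%), as stated. Dividing by 0.92 gives 119.6, so 120 randomised per group.

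The figure reproduces. It uses the unadjusted SD, so it does not rely on any covariate.

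**Model for the gain.** The documents give no correlations and no share of subjects at or above 80, so these are assumptions. Take screening, Week 0 and Week 12 scores as trivariate normal with equal variances, and ignore the HbA1c stratum. Write a for the screening-Week 0 correlation, b for Week 0-Week 12, c for screening-Week 12, and p for the share at or above 80. The dichotomised score correlates with the continuous one by k = φ(z) / √(p(1 - p)), where z cuts off the upper share p.

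Residual variance, as a fraction of the outcome variance:
- Week 0 plus category (protocol model): 1 - (b² + k²c² - 2·b·kc·ka) / (1 - k²a²)
- Week 0 plus continuous screening: 1 - (b² + c² - 2abc) / (1 - a²). Under normality the category then adds nothing more.

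**Middle case** (a = 0.7, b = c = 0.5, p = 25%): z = 0.674, k = 0.734, ka = 0.514, kc = 0.367.
- Protocol model: 1 - (0.250 + 0.135 - 0.189) / (1 - 0.264) = 0.7335
- With continuous screening: 1 - (0.250 + 0.250 - 0.350) / 0.510 = 0.7059
- Reduction: 1 - 0.7059/0.7335 = 3.8%. This equals 220 × (0.7335/0.7059 - 1) = 8.6 subjects out of 220 evaluable, before the degree of freedom is charged.

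**How it depends on c**, other inputs unchanged:

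| Screening-Week 12 correlation | Reduction in residual variance |
|---|---|
| 0.50 (equal to Week 0) | 3.8% |
| 0.45 | 1.7% |
| 0.40 | 0.4% |
| 0.35 (= 0.7 × 0.5) | 0.0% |

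At c = a × b the screening score adds nothing once Week 0 is known.

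**Range.** Take a from 0.6 to 0.8, b from 0.3 to 0.6, c from a × b (nothing beyond Week 0) up to b (as predictive as Week 0), and p from 10% to 50%. The reduction runs from 0% to 10.9%, the top at a = b = c = 0.6 and p = 10%.

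**Cost.** With 220 evaluable subjects and six fitted parameters, one degree of freedom costs about 1/214 = 0.47% of variance. That exceeds the 0.4% gain at c = 0.40.

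**On the power scale**, with 110 per group, p = 30% and the unadjusted SD held at 12.1 (a = 0.7, b = c = 0.5):

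| Model | Residual SD | Power |
|---|---|---|
| SAP 2.1 as written | 11.96 | 81.4% |
| Protocol 13.1.3 | 10.35 | 90.9% |
| Protocol 13.1.3 plus continuous screening | 10.17 | 91.9% |

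In variance terms, restoring Week 0 to the SAP model gives 25.1% and the two steps together give 27.7%. Adding continuous screening to the SAP model without Week 0 gives only 1.7%.

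**Availability of the score.** The SAP's Week -4 window for DTR-QOL is Day -30 to -15, and its Week 0 window starts at Day -14. Protocol 9.2.1 allows the screening questionnaire up to Day -14. Read as printed, a Day -14 questionnaire is not a Week -4 value, and SAP 2.4.2 excludes data not adopted under its handling rules. A covariate taken from the windowed data could therefore lose subjects. The score used for stratification under protocol 8.5 could not.

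**The case against.** The strongest case against is that this is a preference. The category is in the model because randomisation was stratified on it, and adjusting for strata as randomised is standard and valid. The gain rests on correlations that the documents do not give. A score taken two to four weeks before Week 0 may well predict Week 12 less well than Week 0 does, and then the gain shrinks to nothing while the degree of freedom is still spent. The material defect in SAP 2.1 is the missing Week 0 score.

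Most of this stands. The lower limit is zero, the precision is not strictly free, and the Week 0 omission matters far more. What does not follow is that the point should be dropped. Stratification is a reason to keep the category, not a reason to leave out the value behind it. The downside is limited to about 0.5% of variance, and correlation between the two baselines does not harm the arm contrast.

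A reader might go further and infer three things that the documents do not support:
- *That the trial is underpowered.* The 110 per group reproduces from the plan's own inputs without this covariate.
- *That the category biases the result.* Both models give a valid comparison of the randomised arms.
- *That a subject at 30 and one at 79 are treated alike.* In the protocol model the continuous Week 0 score already separates most such subjects. Only SAP 2.1 as written lacks that term.

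**Conclusion.** The point holds as a small efficiency gain. A required pre-drug measurement of the primary outcome is used only as a two-level factor in both documents. Relative to the protocol model, its continuous value is worth 0% to about 11% of residual variance, and about one power point in the central case. The size rests on the assumed correlations, on normality with equal variances, and on screening being no more predictive of Week 12 than Week 0 is. At the low end the net effect can be a very slight loss. It ranks below the missing Week 0 score in SAP 2.1.

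**What to change.** In SAP 2.1:
1. Restore the continuous Week 0 total score, so that the SAP agrees with protocol 13.1.3.
2. Keep both randomisation strata and add the continuous screening total score. Make the same addition in protocol 13.1.3.
3. State that this score comes from the questionnaire used for allocation, not from the SAP's Week -4 window, so that no subject is lost.
4. Fix the model before any outcome data are seen.

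While editing, reconcile the printed raw-score cut. Protocol 8.5 gives 168.2, which is 29 + 0.8 × 174. The study summary gives 139.4, which is (139.4 - 29)/174 = 63.4% on that scale.

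The cost is one more model term and one degree of freedom. No new data, visits or questionnaires are needed.

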2.2 Secondary Endpoints and the Analytical Methods

Analysis Set: Full Analysis Set

Items: 1) DTR -QOL Total Score
2) DTR -QOL Total Score of Factor1 to Factor 4
"Factor 1: Burden on Social Activities and Daily Activities" (13 questions)
"Factor 2: Anxiety and Dissatisfaction with Treatment" (8 questions)
"Factor 3: Hypoglycemia" (4 questions)
"Factor 4: Satisfaction with Treatment" (4 questions)
3) DTSQ Total Score
4) DTR -QOL Total Score of Each Items
5) DTSQ Total Score of Each Items

Analysis Visit: Week 0, Week 4, Week 12, End of Study

Method:

- (1) The following analysis will be performed for the Items 1 to 3 described above.
 Summary statistics of observed value and 95% confidence interval for the mean will be calculated by treatment groups and Analysis Visit. In addition, Mean (+/-SD) plots will be made by treatment group and Analysis Visit. Adjusted mean differences and the 95% confidence interval (two-sided) will also be provided. The same analyses described above will be performed on change from baseline at each analysis visit.
- (2) The following analysis will be performed for the Items 2 to 3 described above.
 Analysis of covariance (ANCOVA) will be conducted to compare between the treatment groups using "the change from baseline in the total score by the end of treatment [the End of Study(Week 12) - baseline (Week 0)]" as a dependent variable; the total score of "the DTR-QOL Total score (<80 or ≥ 80)" at the baseline (Week 0) and "HbA1c (<8.0% or $\geq 8.0\%$)" at the baseline (Week 0) as covariates; and "a treatment group" as an independent variable.
- (3) The following analysis will be performed for the Items 1, 3 described above.
 The summary statistics and two-sided 95% CI for means of change from baseline by treatment group will be calculated, with stratification by the following factors at the start of the treatment period (Week 0):
 - Use of medication for treatment of comorbidities;
 - Number of daily doses of medication for treatment of comorbidities (<2 times or ≥ 2 times);
 - total number of daily tablets of medication for treatment of comorbidities (<2 tablets or ≥ 2 tablets);
 - Number of doses of the study drug or comparative drug (once weekly, once daily or twice daily).
- (4) The following analysis will be performed for the Items 4 -5 described above.
 Summary statistics for measurements and the change from baseline (Week 0) will be calculated by treatment group per question at each analysis visit.

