 - 3) The analyses below carried out on the total score for each factor provided through the DTR-QOL Questionnaire, and on the total score for treatment satisfaction in the DTSQ: A comparison between the treatment groups will be carried out based on the ANCOVA model using "the change in the total score by the end of treatment [the end of the treatment period (Week 12) - baseline (Week 0)]" as a dependent variable; the total score at the baseline (Week 0), the total score of "the DTR-QOL Questionnaire (<80% or \geq 80%)" at the baseline (Week 0) and "HbA1c (<8.0% or \geq 8.0%)" at the baseline (Week 0) as covariates; and "a treatment group" as an independent variable. The level of significance will be 5% (two-sided). Note that the total score for all questions in the DTR-QOL is out of the scope of the analysis.
 - 4) To indicate the changes in the total scores for all questions in the DTR-QOL Questionnaire and the total scores for treatment satisfaction in the DTSQ, the summary statistics and two-sided 95% CI for means per treatment group will be calculated, with stratification by the following factors at the start of the treatment period (Week 0):
 - Use of medication for treatment of comorbidities
 - Number of daily doses of medication for treatment of comorbidities (<2 times or \geq 2 times)

- Total number of daily tablets of medication for treatment of comorbidities (<2 tablets or ≥ 2 tablets)
- Number of doses of the study drug or comparative drug (once weekly, once daily or twice daily)
- Changes in the scores per question in the DTR-QOL Questionnaire at each assessment time point.
- Changes in the scores for per question in the DTSQ at each assessment time point.
 - 1) Summary statistics for measurements and the changes from the baseline (Week 0) will be calculated per treatment group.

<Other endpoints>

Summarizations below will be performed in the "full analysis set" (FAS).

- Laboratory tests
Treatment compliance of each study subject will be calculated and summary statistics of compliance per treatment group will be presented.
- Treatment compliance
Treatment compliance of each study subject will be calculated and summary statistics of compliance per treatment group will be presented.
- The Basic Information on Study Subject (Your Basic Profile)
Frequency of answers to each question at each visit will be analyzed per treatment group.

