2.4 CONSIDERATIONS on STATISTICAL ANALYSIS

2.4.1 Adjustments for Covariates

ANCOVA will be performed on primary and secondary endpoints using treatment group as independent variables. Details are described in 2.1 and 2.2

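### SAP 2.2 Method (1) promises adjusted arm differences for the DTR-QOL and DTSQ scores at every visit but names no model, where protocol 13.1.3 describes differences without covariates

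*SAP*

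**What the plan says.** Protocol 13.1.3, secondary efficacy endpoints, step 1) asks for summary statistics by arm at each time point and adds: "Point estimates and the two-sided 95% CI for differences between the treatment groups will also be calculated". Step 2) extends this to change scores: "Changes from the baseline (Week 0) to each assessment time point will be calculated to be similarly analyzed to 1) above". Neither step names a covariate. ANCOVA comes separately, in step 3), for change to Week 12 in the factor scores and the DTSQ. Its covariates are the continuous Week 0 score and the Week 0 categories of DTR-QOL and HbA1c. The DTR-QOL total is left out of that step: "Note that the total score for all questions in the DTR-QOL is out of the scope of the analysis".

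SAP 2.2 Method (1) covers the same scores (Items 1 to 3) and states: "Adjusted mean differences and the 95% confidence interval (two-sided) will also be provided". The section has one visit list, "Analysis Visit: Week 0, Week 4, Week 12, End of Study", and then adds: "The same analyses described above will be performed on change from baseline at each analysis visit". No covariates are given. The ANCOVA in Method (2) is restricted: "The following analysis will be performed for the Items 2 to 3 described above". It concerns change to End of Study (Week 12). SAP 2.4.1 says only "ANCOVA will be performed on primary and secondary endpoints using treatment group as independent variables" and refers back to 2.1 and 2.2. For laboratory tests, SAP 2.3 asks for mean differences without calling them adjusted.

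**The concern.** The two documents describe the same table entry differently, and the SAP's description cannot be programmed as written. Because the SAP omits the word adjusted for laboratory tests, its use in 2.2 looks deliberate. Someone therefore has to choose the covariates, and the text does not say which.

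At stake are the Week 4 and Week 12 arm differences for the patient-reported scores. The trial is open-label and SAP 2.4.5 makes no multiplicity adjustment, so secondary estimates are best fixed before the data are seen. Some of the candidate models also give up precision that the Week 0 score, already collected, would supply.

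**Working it through.** **Which estimates have a model.** Each score has seven non-trivial differences: observed value at four visits and change at three (change at Week 0 is zero for everyone).

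- End of Study change: SAP 2.1 for the total (screening categories of DTR-QOL and HbA1c); SAP 2.2(2) for factors and DTSQ (Week 0 categories). Neither has the continuous Week 0 score.
- Week 12 change: covered only if the SAP's label End of Study (Week 12) is read to include the Week 12 window.
- Week 4 change, and observed values at Week 4, Week 12 and End of Study: no model.
- Observed value at Week 0: no model. Adjusting for the Week 0 score itself gives zero by construction; adjusting a score for its own Week 0 category has no useful meaning.

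So one of seven has a model, or two on the wider reading.

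**The plan's own figure.** Protocol 13.3 gives mean changes of 19.0 and 14.4 (difference 4.6), SD 12.1, two-sided 5%, 80% power and 110 per group.

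- Normal approximation: n = 2 × (1.960 + 0.842)² × 12.1² / 4.6² = 108.6, so 109.
- Two-sample t: power is 0.7979 at 109 and 0.8015 at 110, so 110.
- Dropout: 110 / 0.92 = 119.6, so 120.

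The plan's figures reproduce, and the calculation is itself an unadjusted comparison.

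**Precision for change in the total.**

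- Plain: SE = 12.1 × √(2/110) = 1.63; 95% half-width 1.96 × 1.63 = 3.20.
- Continuous Week 0 score: with equal variances at both visits and visit correlation r (not in the documents), the residual SD is 12.1 × √((1 + r)/2). The half-width is 3.20 × √0.65 = 2.6 at r = 0.3, 3.20 × √0.75 = 2.8 at r = 0.5 and 3.20 × √0.85 = 2.9 at r = 0.7. Simulation with stratified allocation gives 2.5 to 2.9.

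**Gap between plain and adjusted change estimates in one trial.** Without stratification its SD is SE × √R², where R² = (1 − r)/2 for the continuous Week 0 score: 1.63 × √0.35 = 0.97, 1.63 × √0.25 = 0.82 and 1.63 × √0.15 = 0.63. The simulations used 110 per arm, a true difference of 4.6 and allocation stratified on the screening factors. Their ranges cover visit correlations of 0.3 to 0.7 and, as an alternative set-up, baseline-to-change correlations of −0.3 to −0.7:

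| Adjustment | SD of (adjusted − plain), points |
|---|---|
| Screening categories (as SAP 2.1) | 0.02 to 0.1 |
| Week 0 categories (as SAP 2.2(2)) | 0.3 to 0.8 |
| Continuous Week 0 score plus screening strata | 0.4 to 1.0 |

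The screening categories change almost nothing because allocation is balanced on them. In the alternative set-up the mean estimate was about 4.6 under every model. Whether the interval excluded zero differed from the plain analysis in 0.4 to 4.5%, 4 to 11% and 5 to 16% of trials for the three rows.

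**The case against.** The protocol never calls its difference unadjusted, and protocol 13.1 leaves detailed methods to the SAP. On that view this is one undefined word in a secondary summary. Protocol 13.0 also gives the analysis to a CRO independent of the sponsor, which limits the room for selection. Part of this stands. The unadjusted reading is an inference from the layout: summary statistics in steps 1) and 2), a separate ANCOVA in step 3), and the total excluded from it. But if the SAP is where the method is to be defined, SAP 2.2(1) is where it is missing.

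A reader might infer three stronger things that the documents do not support.

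- That no SAP model fits at all. End of Study change does have one.
- That the conflict is worth 1.3 to 1.8 points. In simulation that is the SD of the gap between observed-value and change-score differences, at visit correlations of 0.3 to 0.7. Both scales are prespecified in both documents, so that gap is not a disagreement between them. The plain-versus-adjusted gap is smaller.
- That the figures hold for every listed score. The 4.6 and 12.1 are assumptions for the DTR-QOL total; the documents give no SD for the factors or the DTSQ.

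It is also fair to say that adding a screening-strata ANCOVA to Method (1) alone would clash with the Week 0 categories in SAP 2.2(2) and protocol 13.1.3 3). The remedy has to cover those as well.

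**Conclusion.** The mismatch is real and limited. Protocol and SAP describe the secondary arm differences differently, and outside End of Study (Week 12) change the SAP gives no model for its version. Under randomization all the candidate estimators target the same quantity, so neither bias nor harm to the primary test follows. What follows is lost precision and an estimate not settled in advance. For the DTR-QOL total, the choice moves the change estimate with an SD of about 0.02 to 1.0 points, against an assumed effect of 4.6. It also moves the 95% half-width between about 3.2 and 2.5 to 2.9. These sizes rest on 110 per arm, an SD of change of 12.1 and assumed correlations. For the factors and the DTSQ the size cannot be stated. The point should be corrected.

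**What to change.** In SAP 2.2(1), define the adjusted difference for Items 1 to 3 at Week 4, Week 12 and End of Study as the ANCOVA difference with these covariates: the item's own continuous Week 0 score, the screening DTR-QOL stratum (<80 or ≥80) and the screening HbA1c stratum (<8.0% or ≥8.0%). With the continuous Week 0 score in the model, observed-value and change analyses give the same arm difference, so one figure per visit is enough.

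Use the same covariates in SAP 2.2(2) and protocol 13.1.3 3), so that each item has one ANCOVA difference at End of Study, and align protocol 13.1.3 1) and 2). For the total, these are already the covariates of the protocol's primary ANCOVA; SAP 2.1 has to list the continuous Week 0 score too, or the total will carry two End of Study figures. Keep observed-value and change summaries by arm as descriptive, and give no adjusted difference at Week 0.

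The cost is a few lines in both documents and no new data; the protocol's plain differences become descriptive only. Deleting the word adjusted from SAP 2.2(1) would also end the conflict, but would keep the wider intervals.
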